#### 3.5. Study visits/Follow-up

No study visits or follow up will be needed for this study. The subject participation will be considered complete when the subject and her child are discharged from the hospital.

#### 3.6. Withdrawals

Subjects who withdraw from the study after randomization will be excluded from further follow-up. Outcomes ascertained up until the time of withdrawal will be reported in an intent to treat fashion. Those who withdraw prior to determining the primary outcome will be accounted for by randomizing an equal number of additional subjects.

# 3.7 Outcomes

# Primary outcome:

• Proportion of undelivered subjects at day 7 from the diagnosis of PPROM

# Secondary outcomes:

• Latency defined as time interval from PPROM to delivery

Data to be collected will consist of demographics, obstetrical history, relevant vital signs and laboratories. Examples of data to be collected but not limited to include: age, ethnicity/race, gravida, para, received tocolytics, received antenatal steroids, gestational age at rupture of membranes, reason for delivery, mode of delivery, gestational age at delivery, chorioamniotis, date & time of initiation of antibiotics, date & time of delivery, placental abruption, hospital length of stay, number of women undelivered at day 7 of admission, NICU admission, infant intubation days, neonatal NEC and neonatal sepsis.

In addition, drug adverse effects profiles between the two will be assessed in a post treatment patient survey. The latter will be assessing the severity and incidence of diarrhea and other symptoms such as nausea and vomiting and their severity.

# **Study Summary Flow Diagram**

# 5- **Criteria for inclusion of subjects:**

- Maternal age  $\geq$  18 years and <50 years
- Pregnant women between the gestational age 23 6/7 and 32 6/7 weeks
- Singleton pregnancy
- Preterm premature rupture of membranes, determined clinically
- Cervical dilation visually  $\leq$  5cm on sterile speculum exam.

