#### 3.1 Screening, Recruitment and Consenting:

Under the direction of the PI, trained research staff will be available 24/7 to screen and consent subjects according to study protocol. Medical records of all potential subjects with a diagnosis of PPROM will be reviewed and those who satisfy inclusion and exclusion criteria will be approached and a written informed consent will be obtained. A screening log will be used to track all subjects approached for the study. Potential subjects may be patients of the investigators.

Subjects will be enrolled at the time of admission to labor and delivery (L&D) or thereafter. Subjects will be recruited, enrolled and consented in a private room in labor and delivery or antepartum units in order to respect the privacy of potential subjects. Subjects will be given all the time needed in order to fully understand and read the consent forms. All questions will be fully answered. If needed, a certified language interpreter will be available and Spanish consents will be used as appropriate. Women will only be randomized on our labor and delivery or antepartum units when the decision to initiate antibiotics is made, AND they continue to be eligible (using a randomization screen).

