# 6- Criteria for exclusion of subjects:

- Intrauterine fetal demise (no fetal heart beat identified and documented by two physicians)
- Any contraindication to expectant management (e.g. fetal compromise, chorioamnionitis, placental abruption)
- Cervical cerclage in place
- Placenta previa or other known placental anomalies
- Contraindication to any of the antibiotics used (allergy to macrolides).
- Enrolled in another trial that may affect outcome.
- Clinical chorioamnionitis or any other active bacterial infection (e.g. pyelonephritis, pneumonia, abscess) at time of randomization: because standard antibiotic therapy for these conditions may confound trial intervention.
- No prenatal care (less than 2 prenatal visits)
- Non-resident subject who is unlikely to be followed-up after delivery
- Any fetal congenital anomaly.
- Significant liver disease defined as known cirrhosis or elevated transaminases of at least 3-fold upper limit of normal
- Significant renal disease defined as serum creatinine known to be >2.0 mg/dl or on dialysis.
- Active congestive heart failure (EF<45%) or pulmonary edema.
- Immunosuppressed subjects: i.e., taking systemic immunosupressants or steroids (e.g. transplant subjects; not including steroids for lung maturity), HIV with CD4<200, or other.
- 7- **Sources of research material**: Electronic medical records and subject survey.
- 8- Recruitment Methods and Consenting Process:

Please refer to section 3.1 above.

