# 12-Potential benefits:

In the background of erythromycin nationwide shortage, this will be the first level 1 trial to show that azithromycin may be equivalent to erythromycin in delaying delivery in patients with PPROM. This study may show for the first time that current alternative practice with azithromycin is as effective as erythromycin but with less adverse effects, less costly and easy administration.

13-**Statistical approach:** Analysis will be performed by intent to treat. Univariable analysis (such as t-test, Mann-Whitney or Chi-square) will be used for descriptive statistics such as patient demographics and assessment of primary outcome. Multivariable logistic analysis will be used to account for potential confounding variables. Sample size was calculated using a noninferiority trial design. Azithromycin will be tested against erythromycin for PPROM. The primary outcome will be the proportion of subjects undelivered

by day 7. For the sample size calculation, it is assumed the proportion undelivered in the erythromycin group would be 70% (pi = 0.7) based on Haas et al study. We considered that a difference in undelivered rate as large as 15% in favor of erythromycin would allow azithromycin to be non-inferior (delta = 0.15). This study will use 80% power to confirm non-inferiority and a one-sided confidence level of 97.5%.

Estimated sample size for two-sample comparison of proportions (non-inferiority)

Null hypothesis: p2 - p1 � delta (inferior), where:

pi (entered in command) is the overall proportion of participants expected to experience the outcome if the treatments are non-inferior, and delta is the smallest change in proportions between groups (p2 - p1) which would still be clinically important.

Alternative hypothesis: p2 - p1 < delta (non-inferior)

Note: a non-inferiority analysis is one-sided.

```
Assumptions:

power = 0.8000

alpha = 0.0250 (one-sided)

pi = 0.7000

delta = 0.1500

estimated required sample size (per group) = 147
```

The total estimated sample size is 294. Assuming 10% loss to follow, this study proposes a total of 324 subjects will be needed to complete the study. The STAT 14 (Dallas, Tx) will be used for statistical computations. This trial will be registered with Clinical Trials Register (Clinicaltrials.gov), before recruitment is initiated and after IRB approval."

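### Women dilated up to 5 cm may enter and labour is not explicitly excluded, yet the day-7 analysis gives dilation and labour status no stated role, so a true deficit could be diluted unseen

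*Combined protocol and SAP*

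**What the plan says.** **Entry.** Section 5 of the combined protocol and SAP includes women with "Cervical dilation visually $\leq$ 5cm on sterile speculum exam". No criterion in section 5 or 6 names labour or contractions. The nearest exclusion in section 6 is open-ended: "Any contraindication to expectant management (e.g. fetal compromise, chorioamnionitis, placental abruption". Section 3.1 randomises women "when the decision to initiate antibiotics is made, AND they continue to be eligible", with no separate check for labour.

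**Outcome and analysis.** The primary outcome in section 3.7 is "Proportion of undelivered subjects at day 7 from the diagnosis of PPROM". Section 13 (Statistical approach) states that "Sample size was calculated using a noninferiority trial design", with an absolute margin of 15 percentage points, one-sided alpha 0.025, 80% power and analysis by intent to treat. It assesses the primary outcome with univariable methods. It then adds that "Multivariable logistic analysis will be used to account for potential confounding variables" and does not name the variables. It plans no subgroup, restricted or sensitivity analysis by dilation or labour.

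**Data.** The examples of data to be collected in section 3.7 include "age, ethnicity/race, gravida, para, received tocolytics, received antenatal steroids, gestational age at rupture of membranes, reason for delivery". Dilation and labour status at entry are not among the examples, but the list is stated to be open.

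**The concern.** The stated objective is to compare how well the two regimens prolong pregnancy. A woman who will deliver before day 7 whichever macrolide she receives contributes a failure in either arm. She carries no information on the difference between the drugs, but she counts in the denominator.

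If azithromycin is truly worse in the other women, their deficit is scaled down by the share of such women enrolled, while the 15-point margin stays where it is. A finding of non-inferiority could then owe something to who was enrolled. If labour status is not recorded at randomisation, nobody can judge afterwards how large that group was.

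The protocol itself treats dilation as relevant, since it caps it at entry, but gives it no stated use after that.

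**Working it through.** **Inputs from section 13.** Proportion undelivered on erythromycin 0.70; margin 0.15; one-sided alpha 0.025 (z = 1.960); power 0.80 (z = 0.842); 147 per group.

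**Assumed input.** f is the share of women who deliver before day 7 whichever macrolide is given. The documents give no value, so a range is shown.

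**Step 1: reproduce the plan's sample size.** n per group = (1.960 + 0.842)² × 2 × 0.70 × 0.30 / 0.15² = 146.5, rounded up to 147, or 294 in total. This matches the plan. Power at 147 per group is 80.1%.

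**Step 2: dilution.** Let the other women have 70% undelivered on erythromycin and 70% − D on azithromycin. Over all enrolled women:

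- erythromycin: pE = 0.70(1 − f)
- azithromycin: pA = (0.70 − D)(1 − f)
- observed deficit: pE − pA = (1 − f)D

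The chance of declaring non-inferiority is Φ[(0.15 − (1 − f)D)/SE − 1.960], with SE = √{[pE(1 − pE) + pA(1 − pA)]/147}.

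**Step 3: a 15-point deficit in the other women (D = 0.15, that is 70% v 55%).**

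| f (assumed) | pE | pA | Observed deficit (points) | SE | Declared non-inferior |
|---|---|---|---|---|---|
| 0% | 0.700 | 0.550 | 15.0 | 0.0558 | 2.5% |
| 5% | 0.665 | 0.5225 | 14.25 | 0.0567 | 3.4% |
| 10% | 0.630 | 0.495 | 13.5 | 0.0573 | 4.5% |
| 20% | 0.560 | 0.440 | 12.0 | 0.0579 | 7.5% |
| 30% | 0.490 | 0.385 | 10.5 | 0.0575 | 11.9% |

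For example, at f = 10%: (0.15 − 0.135)/0.0573 − 1.960 = −1.698, and Φ(−1.698) = 0.045.

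Put another way, an observed deficit of 15 points corresponds to D = 0.15/(1 − f) in the other women: 15.8, 16.7 and 18.8 points at f = 5, 10 and 20%.

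**Step 4: equal drugs (D = 0), with 70% applying only to the other women.** The observed difference is zero and only the variance changes. Power is 80.1% at f = 0 and 77.8, 75.9 and 73.6% at f = 5, 10 and 20%.

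**Step 5: sensitivity to what the 70% means.** Suppose 70% is the rate over all enrolled women on erythromycin, so that pE = 0.70 and pA = 0.70 − 0.15(1 − f). The probabilities corresponding to step 3 are then 3.4, 4.5 and 7.8% at f = 5, 10 and 20%, almost unchanged. The loss of power in step 4 disappears and power stays at 80.1%.

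**The case against.** **The trial is pragmatic, and its alpha refers to everyone enrolled.** This stands. A reader might infer from step 3 that the type I error is inflated above the stated 2.5%. It is not. If the difference in the enrolled population is 13.5 or 12.0 points, it lies inside the margin, and declaring non-inferiority is correct under the plan. The figures describe what that conclusion would mean for women whose outcome the macrolide can affect.

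**The direction is conditional.** This also stands. It is tempting to say that these women always favour non-inferiority. They do so only if azithromycin is truly worse. Under the working hypothesis of no difference, they cost power or change nothing.

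**The erythromycin rate need not fall below 70%.** A reader might infer that it must. Section 13 takes the 70% from a retrospective comparison whose dilation and labour criteria are not described here, so the figure may already include such women.

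**Labouring women may already be kept out.** In part. The exclusion for any contraindication to expectant management is open-ended, and section 3.1 re-checks eligibility at randomisation. Either could remove some of them. But labour is not among the examples given, and a judgement made at several sites cannot be verified unless the status is recorded.

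**The fields may exist.** Fair. The list in section 3.7 is illustrative, and section 4 says that the data forms are attached to the application; they are not part of the text reviewed. The documents therefore do not show that dilation or labour goes unrecorded. Antibiotic and delivery times are listed, so very early deliveries could be identified. What remains is that section 13 pre-specifies no use of any of this.

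**Conclusion.** The concern holds as a point about interpretation and precision. Dilation up to 5 cm is allowed, labour is not explicitly excluded, and the analysis plan gives neither a stated role.

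The size depends wholly on f, which the documents do not give. At 5% the effect is small (3.4% against 2.5%); at 20% it is material (7.5%). These figures assume 147 per arm, a 15-point deficit confined to women whose outcome the drug can affect, and no effect at all in the rest. How many women at higher dilation or in labour would enrol, and how soon they would deliver, cannot be established from the documents.

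The documents do not support the stronger conclusions that the trial's error rate is wrong or that the 5 cm rule is mistaken.

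**What to change.** Leave the entry rule to the sponsor and change the analysis plan in two places.

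1. **Primary comparison.** Replace the univariable test with a covariate-adjusted (standardised) day-7 risk difference. Set its confidence interval against the 15-point margin, and adjust for dilation at entry (in cm) and gestational age at rupture. The second is already in the listed data; the first is assessed for eligibility and needs only to be kept as a value. This gains precision to the extent that the covariates predict delivery. It does not remove dilution, because the target is still the average over all enrolled women.
2. **Supportive comparison.** Record labour status (yes/no) at randomisation, unless the data form already holds it. Pre-specify the same risk difference and interval in women not in labour, reported beside the primary result. Because status is fixed before allocation, the restricted comparison keeps the benefit of randomisation. This is the part that checks for dilution.

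**Cost.** One added field, and a wider interval in the restricted analysis. For illustration, with 70% undelivered in both arms, the 95% half-width is 1.96 × √(0.42/147) = 10.5 points in all women. If 20% were in labour, leaving about 117.6 per arm, it is 1.96 × √(0.42/117.6) = 11.7 points. The restricted analysis should therefore stay supportive. No added patients or procedures are needed.

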# 6- Criteria for exclusion of subjects:

- Intrauterine fetal demise (no fetal heart beat identified and documented by two physicians)
- Any contraindication to expectant management (e.g. fetal compromise, chorioamnionitis, placental abruption)
- Cervical cerclage in place
- Placenta previa or other known placental anomalies
- Contraindication to any of the antibiotics used (allergy to macrolides).
- Enrolled in another trial that may affect outcome.
- Clinical chorioamnionitis or any other active bacterial infection (e.g. pyelonephritis, pneumonia, abscess) at time of randomization: because standard antibiotic therapy for these conditions may confound trial intervention.
- No prenatal care (less than 2 prenatal visits)
- Non-resident subject who is unlikely to be followed-up after delivery
- Any fetal congenital anomaly.
- Significant liver disease defined as known cirrhosis or elevated transaminases of at least 3-fold upper limit of normal
- Significant renal disease defined as serum creatinine known to be >2.0 mg/dl or on dialysis.
- Active congestive heart failure (EF<45%) or pulmonary edema.
- Immunosuppressed subjects: i.e., taking systemic immunosupressants or steroids (e.g. transplant subjects; not including steroids for lung maturity), HIV with CD4<200, or other.
- 7- **Sources of research material**: Electronic medical records and subject survey.
- 8- Recruitment Methods and Consenting Process:

Please refer to section 3.1 above.

#### 9- Potential risks:

#### 7.1. Randomization Risk

Since the antibiotic regimen type will be randomized, it is possible that one or more of the other treatment groups will have more benefit or lower side effects than the group to which subject is assigned.

#### 7.2. Loss of Confidentiality

Any time information is collected, there is a potential risk for loss of confidentiality. Every effort will be made to keep the subject's information confidential; however, this cannot be guaranteed.

# 7.3 Drug Adverse Affects

According to the FDA, Azithromycin is a macrolide and a derivative of erythromycin. Its mechanism of action is mediated by binding to the 50S ribosomal subunit of susceptible bacteria, and inhibiting protein synthesis. Azithromycin targets ureaplasma, aerobic and facultative gram-negative and gram-positive organisms, and some anaerobes. Azithromycin is classified as a pregnancy category B drug – animal studies using maternally toxic doses showed no fetal harm. However, there are no adequate well-controlled studies in pregnant women. It is not known whether azithromycin is excreted in human milk. The only absolute contraindication to its use is a known hypersensitivity reaction to azithromycin, erythromycin or other macrolide antibiotic (quite rare). There are no specific drug-drug interactions warranting dose adjustments when given with other medications. Elimination is by both renal and hepatic route, and no specific adjustments are mandated for subjects with renal or hepatic insufficiency. The long elimination 1/2-life of 68 hours is due to extensive uptake and subsequent release of drugs from tissues.

The FDA does not raise any suspicion that prenatal exposure to azithromycin is associated with long-term adverse outcomes. Animal studies showed that azithromycin did not have mutagenic potential.

Subjects receiving azithromycin may have the following adverse effects:

- a. Rash, increase liver enzymes, kidney dysfunction, neutropenia and thrombocytopenia (rare)
- b. Nausea and vomiting (3%)
- c. Diarrhea (5%)

Subjects receiving erythromycin may have the following adverse effects:

- a. C difficile colitis, increase liver enzymes, confusion, headache (rare)
- b. Nausea and vomiting (25%)

c. Diarrhea (8%)

If any of these risks occur, subjects will be managed according to standard of care based on the symptoms and signs/complaints.

#### **10-Subject Safety and Data Monitoring:**

The collaborators and research coordinator will be responsible for monitoring the safety of this study. The report will include participant demographics, expected versus actual recruitment rates, summary of any quality assurance or regulatory issues, summary of adverse events (AEs) or serious adverse events (SAEs) which may have occurred, and any changes in the protocol as a result of these issues. This report will be prepared yearly and be sent to the PI's. The collaborators and research coordinator will monitor for adherence to consent procedures, inclusion and exclusion criteria, valid abstraction, correct entry, timeliness and responsiveness to data queries. Data collection will be identified with a participant ID number. Data will be collected and stored with the participant ID code only. The master enrollment log linking subject identifiers with study ID numbers will be kept in a password-protected database. Several data collection forms will be used. Data on these forms devoid of personal identifiers will be securely stored at our perinatal research division. The research coordinator and PIs will be available to monitor the data and correct any discrepancies based on source documents if needed.

# 11-Procedures to Maintain Confidentiality:

Each subject will be assigned a study number with personally identifiable information deleted or removed. If needed, charts will be reviewed in the medical records area. Subjects' information will be de-identified and tagged with a number. Data will be collected and stored on a UTMB passwordprotected computer in a locked room.

# 12-Potential benefits:

In the background of erythromycin nationwide shortage, this will be the first level 1 trial to show that azithromycin may be equivalent to erythromycin in delaying delivery in patients with PPROM. This study may show for the first time that current alternative practice with azithromycin is as effective as erythromycin but with less adverse effects, less costly and easy administration.

13-**Statistical approach:** Analysis will be performed by intent to treat. Univariable analysis (such as t-test, Mann-Whitney or Chi-square) will be used for descriptive statistics such as patient demographics and assessment of primary outcome. Multivariable logistic analysis will be used to account for potential confounding variables. Sample size was calculated using a noninferiority trial design. Azithromycin will be tested against erythromycin for PPROM. The primary outcome will be the proportion of subjects undelivered

by day 7. For the sample size calculation, it is assumed the proportion undelivered in the erythromycin group would be 70% (pi = 0.7) based on Haas et al study. We considered that a difference in undelivered rate as large as 15% in favor of erythromycin would allow azithromycin to be non-inferior (delta = 0.15). This study will use 80% power to confirm non-inferiority and a one-sided confidence level of 97.5%.

Estimated sample size for two-sample comparison of proportions (non-inferiority)

Null hypothesis: p2 - p1 � delta (inferior), where:

pi (entered in command) is the overall proportion of participants expected to experience the outcome if the treatments are non-inferior, and delta is the smallest change in proportions between groups (p2 - p1) which would still be clinically important.

Alternative hypothesis: p2 - p1 < delta (non-inferior)

Note: a non-inferiority analysis is one-sided.

```
Assumptions:

power = 0.8000

alpha = 0.0250 (one-sided)

pi = 0.7000

delta = 0.1500

estimated required sample size (per group) = 147
```

The total estimated sample size is 294. Assuming 10% loss to follow, this study proposes a total of 324 subjects will be needed to complete the study. The STAT 14 (Dallas, Tx) will be used for statistical computations. This trial will be registered with Clinical Trials Register (Clinicaltrials.gov), before recruitment is initiated and after IRB approval."

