#### 2- Concise summary of project:

This trial will be a comparative effectiveness pragmatic multi-site randomized trial performed in singleton pregnancies with the diagnosis of PPROM between 24 weeks and 0 days - 32 weeks and 6 days. It will be comparing two well-accepted standardized treatments of care in this subject population: Erythromycin (FDA Category B) versus Azithromycin (FDA Category B). Our primary outcome will be the proportion of women still pregnant by day 7 after the diagnosis of PPROM is made. Our working hypothesis is that there is no measurable difference in the primary outcome between the group randomized to the azithromycin regimen versus the group randomized to the erythromycin regimen. Our secondary outcome will be latency defined as interval from PPROM to delivery. We propose a total of 324 subjects will be needed to complete the study.

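### The stated hypothesis (no difference) and hoped-for conclusion (equivalence) do not match the design, which is a one-sided non-inferiority test with a 15-point margin

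*Combined protocol and SAP*

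**What the plan says.** Three parts of the combined protocol and SAP describe what the trial sets out to establish.

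- Section 2 (Concise summary of project): "Our working hypothesis is that there is no measurable difference in the primary outcome". No direction or margin is attached.
- Section 12 (Potential benefits): "this will be the first level 1 trial to show that azithromycin may be equivalent to erythromycin in delaying delivery". The next sentence adds that the study may show azithromycin to be as effective as erythromycin. Section 1 also describes the evidence gap as a lack of proof of equivalence.
- Section 13 (Statistical approach): "Sample size was calculated using a noninferiority trial design". The margin runs one way only: "a difference in undelivered rate as large as 15% in favor of erythromycin would allow azithromycin to be non-inferior (delta = 0.15". The power statement is explicit about its target: "This study will use 80% power to confirm non-inferiority and a one-sided confidence level of 97.5" per cent. The sample-size output adds "Note: a non-inferiority analysis is one-sided", and the result is 147 per group, 294 in total, raised to 324 for loss to follow-up.

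No section gives an upper limit, a two-sided equivalence margin or an equivalence test. For assessing the primary outcome, section 13 offers univariable tests such as the t-test, Mann-Whitney or chi-square. It does not say that a confidence interval will be compared with -15 points.

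**The concern.** A hypothesis of no difference, a claim of equivalence and a claim of non-inferiority are three different things. The trial is sized for the third. Non-inferiority within 15 points excludes only that azithromycin is worse by 15 points or more. It does not by itself show that the two regimens are equivalent.

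This goes beyond word choice because of how the primary analysis is described. If the hypothesis is no measurable difference and the named test is a chi-square, a reader could take a non-significant p-value as confirming the hypothesis. That criterion does not use the margin, and it gives far weaker protection against accepting a regimen that is worse by the full margin. The 15-point margin appears only in the sample-size text, so nothing in the stated hypothesis prevents this reading.

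**Working it through.** **Inputs from section 13:** 70% undelivered at day 7, margin 0.15, one-sided alpha 0.025, power 80%, 147 per group, total 324 after the allowance for loss. Section 4 gives 1:1 allocation, so 324/2 = 162 per arm. **Assumptions, not in the documents:** an upper equivalence limit of +15 points; 5% per side as an alternative alpha; an uncorrected chi-square at two-sided 5%.

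**1. The plan's own figure.** n per arm = 2 × 0.7 × 0.3 × (1.960 + 0.842)² / 0.15² = 146.5, so 147. This matches. At 147 per arm the standard error of the difference is sqrt(0.42/147) = 0.05345, and power for non-inferiority is Phi(0.15/0.05345 - 1.960) = Phi(0.846) = 80.1%. The stated 80% is right for what it is stated to be.

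**2. Power for equivalence, if it were wanted.** With limits of +/-15 points, a true difference of 0 and 70% in both arms, power = 2 × Phi(0.15/SE - z) - 1. The SE is 0.05345 at 147 per arm and sqrt(0.42/162) = 0.05092 at 162 per arm.

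| Analysed per arm | 2.5% per side (z = 1.960) | 5% per side (z = 1.645) |
|---|---|---|
| 147 | 2 × Phi(0.846) - 1 = 60.3% | 2 × Phi(1.161) - 1 = 75.5% |
| 162 | 2 × Phi(0.986) - 1 = 67.6% | 2 × Phi(1.301) - 1 = 80.7% |

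Exact binomial enumeration with Wald limits gives 60.5%, 75.8%, 68.0% and 80.7% for 147 (2.5%), 147 (5%), 162 (2.5%) and 162 (5%).

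**3. What happens if non-significance is taken as success.** At 147 per arm with 70% on erythromycin:

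- *Azithromycin 55% (truly 15 points worse).* Pooled proportion 0.625. Null SE = sqrt(2 × 0.625 × 0.375/147) = 0.0565. True SE = sqrt((0.21 + 0.2475)/147) = 0.0558. P(non-significant) ≈ Phi((1.96 × 0.0565 - 0.15)/0.0558) = 24%. P(non-inferiority declared) ≈ Phi(0 - 1.96) = 2.5%. Exact enumeration: 24.1% and 2.4%.
- *Azithromycin 60% (truly 10 points worse).* Null SE = sqrt(2 × 0.65 × 0.35/147) = 0.0556. True SE = sqrt((0.21 + 0.24)/147) = 0.0553. P(non-significant) ≈ Phi((1.96 × 0.0556 - 0.10)/0.0553) = 56%. P(non-inferiority declared) ≈ Phi(0.05/0.0553 - 1.96) = 15%. Exact enumeration: 56.2% and 14.4%.

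At the margin itself, reading non-significance as success would accept azithromycin about ten times as often as the test the trial was sized for (24.1/2.4).

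**The case against.** The strongest reply is that the plan already contains the right hypotheses. Section 13 gives a null of inferiority and an alternative of non-inferiority, with the direction, the margin and a one-sided alpha. The sentence in section 2 is a working hypothesis in a summary, and section 12 is a hedged benefits statement that sets no success rule. Much of this stands. It does not remove the mismatch. The section 13 hypotheses appear within the sample-size output and do not say which arm is p1 and which is p2. The analysis sentence names tests of difference, and the one hypothesis stated in the plan's prose has no margin.

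Several stronger readings are tempting and are not supported:

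- *That the 80% power is wrong, or is claimed for equivalence.* Section 13 ties it expressly to non-inferiority, and it reproduces.
- *That the plan promises to show equivalence.* Section 12 says may.
- *That the lack of an upper limit is itself a defect.* A non-inferiority design needs none. The gap matters only if equivalence is claimed.
- *That power for equivalence is simply 60%.* That value depends on an upper limit the documents never give, on 2.5% per side and on 147 analysed per arm.
- *That a positive result could never be consistent with equivalence.* On the assumptions above, about three in four non-inferior results (0.603/0.801 = 75%) would also lie within +/-15 points. The narrower statement is the correct one: non-inferiority alone does not establish equivalence.
- *That a non-inferior result will be reported as equivalence.* No section sets such a rule. The wording permits it but does not require it.

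**Conclusion.** The concern holds as a mismatch between the stated hypothesis, the anticipated conclusion and the test that was sized. The sample size for non-inferiority needs no correction on this point.

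The practical risk is that the no-difference hypothesis is paired with a chi-square. At 147 per arm and 70% on erythromycin, a non-significant result would occur about 24% of the time with azithromycin truly 15 points worse, against 2.4% for the non-inferiority test. These figures assume an uncorrected two-sided 5% chi-square and describe a possible reading, not a rule the plan lays down. Power for equivalence, at 60% to 81%, is indicative only, because both the upper limit and the 5% alternative are assumed. The point is worth settling before analysis, since it bears on what counts as success and costs almost nothing.

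**What to change.** Keep the sample size and make these wording changes:

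- **Section 2.** Restate the hypothesis as: the proportion undelivered at day 7 with azithromycin is not lower than with erythromycin by 15 percentage points or more.
- **Section 13.** State that this is judged by the lower limit of the two-sided 95% confidence interval (one-sided 97.5%) for azithromycin minus erythromycin lying above -15 points. Add that a non-significant test of difference is not evidence of non-inferiority or of equivalence.
- **Section 12.** Limit the anticipated conclusion on delaying delivery to non-inferiority within 15 points.
- **Only if an equivalence statement is also wanted.** Pre-specify both limits and the alpha per side, and state the power. With +/-15 points, a true difference of 0 and 70% in both arms, this is about 60% at 147 per arm and 68% at 162 per arm with 2.5% per side, or about 75% and 81% with 5% per side.

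The cost is a few sentences and no extra participants. The downside is that the claim the trial can make becomes narrower.
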